7.9.4.4 Determination of Patients/Data for Analysis

The Enrolled Population will be included in the analysis.

7.9.5 Secondary objective 4: Referral and implant refusal rationale

Summarize the referral and refusal implant rationale.

7.9.5.1 Hypothesis

There are no hypotheses for this objective, as this is a characterization objective.

7.9.5.2 Endpoint definitions

The outcome measure will be the proportion of patients with ICD indication, who were not referred, refused referral or refused implant. The denominator will count all patients with at least one of the below:

- (a) a reduced ejection fraction, as measured by the Left Ventricular Ejection Fraction (LVEF) being lower or equal than 40%.
- (b) ventricular arrhythmia, AV block, new onset bundle branch block, or conduction abnormalities as measured by ECGs.
- (c) unexplained syncope, clinically significant palpitations or symptomatic bradycardia as assessed by the physician

The numerator will count the patients included in the denominator who were not referred, refused referral or refused implant of an ICD/CRT-D.

7.9.5.3 Analysis methods

At each visit, the reasons for refusing referral (“reasons the subject has not been referred at this visit” in the referral CRF) at each visit will be summarized as displayed in table 8.

Table 8: Reason of referral

Region	Reason for refusal referral	3 months visit	6 months visit	12 months visit
Region 1	Reason 1 Reason 2 ... Reason n	XX/XX (XX.XX%) XX/XX (XX.XX%) ... XX/XX (XX.XX%)	XX/XX (XX.XX%) XX/XX (XX.XX%) ... XX/XX (XX.XX%)	XX/XX (XX.XX%) XX/XX (XX.XX%) ... XX/XX (XX.XX%)
...	Reason 1 Reason 2 ... Reason n
Overall	Reason 1	XX/XX (XX.XX%)	XX/XX (XX.XX%)	XX/XX (XX.XX%)

	Reason 2 ... Reason n	XX/XX (XX.XX%) ... XX/XX (XX.XX%)	XX/XX (XX.XX%) ... XX/XX (XX.XX%)	XX/XX (XX.XX%) ... XX/XX (XX.XX%)
--	-----------------------------	---	---	---

Further, at each visit, among all subjects that were recommended for ICD/CRT-D (ie: answer “yes” to question “did the subject meet an indication for an ICD or CRT-D” in the implant CRF), the proportion of those who refused implant (answer “yes” to the question “did the subject refuse the implant”) will be computed and displayed. The reasons for implant refusal (“reason for implant refusal” in implant CRF) will then be computed and displayed in a table similar to Table 7 above.

7.9.5.4 Determination of Patients/Data for Analysis

The subset of subjects of the Enrolled Population that had a reason for referral as described in Section 7.9.5.2 will be included in the analysis.

7.9.6 Secondary objective 5: Change in LVEF Over Time

Determine how the ejection fraction evolves over the immediate period of post MI.

7.9.6.1 Hypothesis

There are no hypotheses for this objective, as this is a characterization objective.

7.9.6.2 Endpoint definitions

The Left Ventricular Ejection Fraction (LVEF) will be measured acutely post MI (≤ 14 days after MI onset) and chronically (40-90 days). The endpoint will be the change between the acute and the chronic measurement.

7.9.6.3 Analysis methods

Descriptive statistics (e.g.: mean, standard deviation, median, range) will be used to summarize the LVEF during the acute phase and the 3 months visit (chronic phase) post-MI and displayed as shown in Table 9 below and graphically with the use of a scatter plot.

Table 9: LVEF at the Acute and Chronic phases

Region	Acute phase	Chronic phase
Region 1		
Mean ± Standard Deviation	XX.X±XX.X	XX.X±XX.X
Median	XX.X	XX.X
25th Percentile - 75th Percentile	XX.X – XX-X	XX.X – XX-X
Minimum - Maximum	XX-X – XX.X	XX-X – XX.X
Subjects With Measure Available (N,%)	XX (XX.X%)	XX (XX.X%)
Region 2		
Mean ± Standard Deviation	XX.X±XX.X	XX.X±XX.X
Median	XX.X	XX.X
25th Percentile - 75th Percentile	XX.X – XX-X	XX.X – XX-X
Minimum - Maximum	XX-X – XX.X	XX-X – XX.X
Subjects With Measure Available (N,%)	XX (XX.X%)	XX (XX.X%)
...
Overall		
Mean ± Standard Deviation	XX.X±XX.X	XX.X±XX.X
Median	XX.X	XX.X
25th Percentile - 75th Percentile	XX.X – XX-X	XX.X – XX-X
Minimum - Maximum	XX-X – XX.X	XX-X – XX.X
Subjects With Measure Available (N,%)	XX (XX.X%)	XX (XX.X%)

Similar statistics will be provided for subjects with LVEF measured at the 6 months and at the 12 months visits.

Additionally, the proportion of subjects whose LVEF measurement was at most 40% will be computed, in both the acute and chronic phases and shown as displayed in Table 10 below.

Table 10: proportion of subjects with a LVEF≤40% at the Acute and Chronic phases, among all subjects with a LVEF measurement at that visit

Region	Acute phase	Chronic phase
Region 1	XX/XX (XX.XX%)	XX/XX (XX.XX%)
Region 2	XX/XX (XX.XX%)	XX/XX (XX.XX%)
...
Overall	XX/XX (XX.XX%)	XX/XX (XX.XX%)

The average change in LVEF between the acute phase and the chronic phase will be estimated using an ANCOVA method. The model will contain the difference of LVEF between the acute phase and the chronic phase as an outcome and baseline LVEF as covariate, to adjust the estimated difference in LVEF between the two visits by the effect of their baseline measure (eg regression to the mean). A SAS code similar to the example below will be used:

```
ods listing close;
proc glm data = lvef;
by region;
model lvef_diff = lvef_base /solution;
run;
ods listing;
```

Results will be determined separately for each region and will be shown by means of either tables or graphs.

In case there will be enough LVEF data at the 6 months and the 12 months follow-up visits, the ANCOVA model above will be used to investigate the average change in LVEF between the chronic phase and the 6 months visit and between the 6 months visit and the 12 months visit.

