9.3. Schedule of Events

Clinical data will be collected at the Baseline 3 month, 6 month, 12 month, and exit visits. In addition if applicable, clinical data will be collected with an exit or death, as well as unscheduled visits. Device data will be collected from device interrogations on Medtronic devices received during the period between the enrollment and exit until study closure; for non-Medtronic devices, device data will not be collected. Data will be collected using eCRFs using an electronic data management system for clinical studies. In addition to eCRF data, non-eCRF data will be collected including device interrogation files (for Medtronic implanted devices only). Surveys may also be used throughout the study.

Data will be stored in a secure, password-protected database, which will be backed up nightly. Data will be reviewed using programmed and manual data checks. Data queries will be made available to study sites for resolution. Study management reports will be generated by Medtronic to monitor data quality and study progress. At the end of the study, the data will be frozen and retained indefinitely by Medtronic. Data Collection requirements are summarized in the table 2 below.

Table 2 Data Collection and study procedure requirements at subject visit

Study Procedure	Baseline	3 month visit	6 month visit	12 month visit	Study Exit
Patient informed consent	X				
Eligibility Verification (Inclusion/ exclusion assessment)	X				
Subject Demographics	X				
Acute MI information	X				
Medical History	X				
Cardiovascular Medications	X	X			
LVEF measurement	X	X*	X (collect if performed as per SOC)	X (collect if performed as per SOC)	
ECG	X	X (collect if performed as per SOC)	X (collect if performed as per SOC)	X (collect if performed as per SOC)	
Referral Status		X	X	X	X
Implant Status (if applicable)		X (if subject receives or has received device implant)	X (if subject receives or has received device implant)	X (if subject receives or has received device implant)	X (if subject receives or has received device implant)
Device Interrogation File (pdd) or CareLink Transmission for subjects implanted with Medtronic device only		X	X	X	X
Adverse Event	As they occur				
System Modification					
Study Deviation					
Subject Death					

* The LVEF measurement needs to be performed ≥ 40 days post-acute MI for MI subjects without revascularization, or ≥ 90 days post-revascularization for post-MI subjects with revascularization done.

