9.6. Follow-Up Visits

Table 3 below specifies permitted time windows for the required subject visits. Subject visit target dates and windows for each follow-up will be made available to the study site. Follow-up visit windows are based on days post-acute MI, and the follow-up visit can be performed either in person or via phone. If a subject visit fall outside the pre-specified window, a study deviation must be reported and the original follow-up schedule maintained for subsequent visits.

Data analyses will include follow-up visits, regardless of whether the visits occur within the time window. Therefore, a late visit is preferred over a missed visit but must be accompanied by a deviation.

Table 3: Follow-up windows

Study Follow-up Visit	Window (Calculated days post-acute MI)		
	Window Start (days post-MI)	Target (days post-MI)	Window End (days post-MI)
3 month	40	90	120
6 month	150	180	210
12 month	335	365	395

Complete a Subject Visit CRF for each follow-up visit.

At 3-month follow-up visit, LVEF will be assessed as per standard practice:

- As per Investigator's discretion, if the subjects have LVEF $\leq 40\%$ or meeting one of the referral criteria (sustained VT, cardiac or unexplained syncope, clinically significant palpitations, new onset bundle branch block, conduction abnormalities, or symptomatic bradycardia), the subjects can be referred for SCD risk stratification and management (EP Referred Group). If the referral does not take place, it is not a study deviation.
- If the subjects have LVEF $>40\%$ but $<50\%$ (between 41% - 49%), the subjects will remain in the Non-Referred Group.
- If the subjects have LVEF $\geq 50\%$, they shall be exited from the study.

For the Non-Referred Group, a Referral Status CRF is needed for each subsequent visit unless the subject is referred to the EP Referred Group. During study follow-up visits, the Non-Referred Group subjects can be referred to the EP Referred Group if their LVEF is $\leq 40\%$ or meets one of the referral criteria (as listed above).

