9.7. Study Exit

At 3-month follow-up, if a subject has an LVEF $\geq 50\%$, the subject will be exited from the study. Subject who remain in the study after 3-month follow-up should remain in the study until the 12-month follow-up is completed or until all data required to meet study objectives have been collected (whichever comes first). Either an in-office visit or phone call is required for study exit.

A study exit eCRF is required for all subjects. Prior to exiting a subject from the study, it is recommended to follow the subject until all AEs are resolved. Following exit, subjects will continue to receive standard medical care. Upon exiting from the study, no further study data will be collected or study visits will occur for the subject. Exited subjects will not be replaced with newly enrolled subjects.

Subjects are urged to remain in the study as long as possible, but may be exited from the study for any of the following situations:

- Study closure
- Subject lost to follow-up (refer to Section 9.11.1)
- Subject did not meet inclusion/exclusion criteria
- Subject did not provide consent or data use protection authorization
- Subject chooses to withdraw (refer to section 9.11.2 for more information)
- Investigator deems withdrawal necessary (e.g. medically justified, inclusion/exclusion criteria not met)
- Subject exited study at the 3 months visit if the 3-month LVEF is $\geq 50\%$
- Subject completed study after 12 months visit
- Subject Death

For study exit visits the following information is required:

- Reason for exit
- Final interrogation file (or CareLink transmission) for subjects implanted with Medtronic device
- Cardiovascular Adverse events, Study Deviations and System Modification

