7.9.6.4 Determination of Patients/Data for Analysis

At each visit, the subset of subjects part of the Enrolled Population with a LVEF measurement available at baseline and at the 3 months visit will be included in the analysis.

8. Safety Evaluation

Relatedness of adverse events using the CEC adjudication will be summarized using counts and percentages. Seriousness of adverse events using the Medtronic classification will be summarized using counts and percentages. Details of individual adverse events will be listed.

9. Changes to Planned Analysis

Any deviation from the analyses described in the statistical analysis plan and a justification for making the change, will be described in the clinical study report. Further, spurious data will be detected and fixed by data management, unused data will be reported in listings, missing data will be reported as count/percentage.

10. Validation Requirements

To ensure the quality of the statistical results and datasets created for the study, the following validation requirements will be implemented.

Programs that contribute directly or indirectly to results pertaining to the primary objective will be validated level I or level II by a statistician or a statistical programmer. Level II or Level III validation (self-validation) will be acceptable for programs, which do not pertain to the primary objective. The table below specifies the validation requirements for data extraction, mapped datasets, analysis datasets, TLGs (Tables, Listings, and Graphs) and study objectives. Mapped datasets are considered as datasets that map case report forms. Analysis datasets are considered to be datasets that contain derived variables relevant for the statistical analysis.

Table 11: Validation requirements

Program type	Level	Description
Extracts or creates datasets, e.g., mapped datasets	II	peer review
Generates analysis datasets	II	peer review
Generates Tables, Listings and/or Graphs (primary objective)	I or II	independent programming or peer review
Generates Tables, Listings and/or Graphs (non-primary objective)	II or III	peer review or self-validation
Implements statistical procedure	II or III	peer review or self-validation
Any other program	II or III	peer review or self-validation
Program previously validated with minor changes	III	self-validation

Summary of Changes

Version	Effective Date	Summary of Changes	Change Author
1.0	06-06-19	Initial Release

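### LVEF at 6 and 12 months comes only from non-recovered, re-imaged subjects, so the planned later summaries and the 3-to-6-month change can show a shift when LVEF is stable

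*SAP*

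**What the plan says.** **Planned analyses.** SAP 7.9.6.3 describes LVEF in the acute and chronic phases (Table 9), then adds: "Similar statistics will be provided for subjects with LVEF measured at the 6 months and at the 12 months visits". It models the acute-to-chronic difference with baseline LVEF as covariate, naming regression to the mean as the reason. If there are enough later data (no threshold is given), "the ANCOVA model above will be used to investigate the average change in LVEF between the chronic phase and the 6 months visit", and the same is planned from 6 to 12 months. Protocol 12.3.5.3 plans the later summaries but not the later ANCOVA.

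**Analysis set.** SAP 7.9.6.4 takes subjects "with a LVEF measurement available at baseline and at the 3 months visit will be included in the analysis". Protocol 12.3.5.4 uses whoever has LVEF at the time point.

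**Who can have later LVEF.** Under Protocol 9.6, for subjects at 50% or above at 3 months, "they shall be exited from the study". Protocol 9.7 repeats the rule and adds: "Upon exiting from the study, no further study data will be collected or study visits will occur for the subject". SAP 7.9.1.3 applies the exit even when another referral reason is present. For those who stay, Protocol Table 2 marks LVEF at 6 and 12 months as "X (collect if performed as per SOC", and Protocol 9.6 allows follow-up by phone.

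**Missing data.** Protocol 12.5 imputes nothing, and under SAP 7.4 the main analyses do not account for missing data.

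**The concern.** The 3-month summary includes recovered subjects; the 6- and 12-month summaries exclude them by rule. Selection is on the outcome itself, and it distorts two planned results in opposite directions:

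- Set against the chronic-phase mean, the 6-month mean is lower because the highest values have been removed.
- Within retained subjects, the 3-to-6-month change is upward, because they were kept for a low 3-month reading and part of that reading is measurement error or short-term variation.

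Neither needs any real change in LVEF. Reported without a label, the first looks like late deterioration and the second like late recovery. The evolution of LVEF is part of the study's stated rationale (Protocol 6.2, SAP 5.3). The analysis set adds to the problem: baseline plus 3-month LVEF is not the pair needed for a 3-to-6 or a 6-to-12-month contrast. It is also unclear whether the baseline in the reused ANCOVA is acute LVEF or the value at the start of the interval.

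**Working it through.** The documents give no expected LVEF values and no figure for 6 or 12 months, so there is no plan figure to reproduce. The check asks what the planned outputs return when LVEF does not change after 3 months.

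**Inputs from the documents:** exit at a 3-month LVEF of 50% or more; no data after exit.

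**Assumptions:** observed 3-month LVEF is normal with mean μ and SD σ of 43/8, 45/9 or 47/10; measurement error is independent at each visit with SD e of 3 or 5 points; re-imaging is at random among those retained.

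**Formulas.** With b = (50 − μ)/σ:

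- proportion exiting = 1 − Φ(b)
- retained 3-month mean k = μ − σ·φ(b)/Φ(b)
- reliability r = 1 − e²/σ²
- 6-month mean of retained subjects m = μ + r(k − μ)

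**Example, 45/9 with e = 5.** b = 5/9 = 0.556; exit = 1 − 0.711 = 28.9%; k = 45 − 9 × 0.3419/0.7107 = 40.67; r = 1 − 25/81 = 0.691; m = 45 − 0.691 × 4.33 = 42.01. Against all subjects at 3 months: 42.01 − 45 = −2.99. Within retained subjects: 42.01 − 40.67 = +1.34.

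| μ/σ | Exit | Retained 3-month mean | 6-month mean (e = 3; 5) | Versus all at 3 months | Own 3-to-6-month change |
|---|---|---|---|---|---|
| 43/8 | 19% | 40.3 | 40.7; 41.4 | −2.3; −1.6 | +0.4; +1.1 |
| 45/9 | 29% | 40.7 | 41.2; 42.0 | −3.8; −3.0 | +0.5; +1.3 |
| 47/10 | 38% | 40.8 | 41.4; 42.4 | −5.6; −4.6 | +0.6; +1.5 |

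Simulation with 2,000,000 subjects per scenario agrees. With e = 0 the paired change is zero, but the fall across visits remains (−2.7, −4.3 and −6.2).

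**Link to the SAP's planning figure.** SAP 6.1 assumes 30% have any referral reason at 3 months, an upper bound for the share at or below 40%. Setting that share to 30% with σ = 10 gives a mean of 45.2 and 31.7% exiting. With e = 5 the fall is 3.9 points and the paired rise +1.3. Over σ of 8 to 12, e of 3 to 7 and a share of 20% to 30%, the fall runs from 0.8 to 9.0 points and the paired rise from 0.4 to 3.4.

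**ANCOVA.** A one-group regression of change on a covariate, evaluated at that covariate's own sample mean, returns the raw change whichever covariate is used. With 3-month LVEF as covariate in the 45/9, e = 5 case, the slope is r − 1 = −0.309 and the intercept 0.309 × 45 = 13.89. At the retained mean of 40.67 the fit is +1.34; at the all-subject mean of 45 it is 0. In all six scenarios the simulated value at the all-subject mean was within 0.01 of zero.

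**6 to 12 months.** The exit rule alone gives a change of 0.00 (within 0.01) in all six scenarios. In the σ = 10, 30% calibration, with 6-month imaging at 70% for a 3-month LVEF at or below 40% and 30% above it, and 12-month imaging at 70% or 30% by the same cut on the 6-month value, the change is +0.4, +0.9 and +1.7 for e = 3, 5 and 7.

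**The case against.** **This is peripheral.** The objective is LVEF over 3 months and the endpoint is the acute-to-chronic change. The later ANCOVA is optional, and nothing is tested. This stands, and it limits the weight of the point.

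**Much is already disclosed.** The later summaries are worded for subjects with a measurement, Table 9 counts those measured, and SAP Table 2 counts exits for LVEF of 50% or more. Table 9 has only acute and chronic columns, so a side-by-side display of later visits is presumed. This stands in part: counts do not tell a reader that the later group was cut off by rule at 50%.

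**The ANCOVA can be made valid.** Selection is on the observed 3-month value, so a regression on that value, evaluated at the all-subject mean, is not biased by the exit. This stands, so dropping the model is one option, not a necessity. The SAP, however, names neither the covariate for the later intervals nor the evaluation point.

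**Stronger readings to avoid.** A reader might infer any of the following; the documents do not support them:

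- *Both later changes are biased by the exit.* The 6-to-12-month change shifts only if re-imaging depends on the 6-month value or clinical course.
- *The share at or below 40% will appear to rise after 3 months.* SAP Table 10 plans that share for the acute and chronic phases only.
- *The later ANCOVA is fixed on acute LVEF.* The wording leaves this open.
- *No other subject can have later LVEF.* Someone without a 3-month LVEF could stay and be imaged later, although SAP 7.9.6.4 leaves such a subject out.

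**Conclusion.** The concern holds for the 6- and 12-month summaries and the 3-to-6-month change. With stable LVEF, and under the assumed distributions (43/8 to 47/10, measurement SD 3 to 5), the 6-month mean lies about 1.6 to 5.6 points below the 3-month mean of all measured subjects, while the retained subjects' own change is about +0.4 to +1.5. The directions follow from the exit rule, although the paired rise needs some measurement error or short-term variation. The sizes rest on assumed SDs and on random re-imaging; selective imaging under standard care would alter them by an unknown amount.

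The 6-to-12-month change is not shifted by the exit rule alone, but it describes only non-recovered, re-imaged subjects and is not a cohort average. The acute-to-chronic endpoint and the primary endpoint are not affected by the exit rule. This is a worthwhile, inexpensive correction to a secondary and partly conditional analysis.

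**What to change.** In SAP 7.9.6.3 and 7.9.6.4:

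1. Present 6- and 12-month LVEF in a separate table for subjects with a 3-month LVEF below 50% and an LVEF at that visit. Show the same subjects' acute and 3-month values and the numbers retained and imaged. Label it as applying to non-recovered, re-imaged subjects, and note that a paired 3-to-6-month rise can reflect regression to the mean; showing the same subjects does not remove that.
2. Either drop the 3-to-6-month ANCOVA, or fit it with 3-month LVEF as covariate and evaluate it at the mean 3-month LVEF of all subjects measured at 3 months. State that this removes selection by the exit rule but relies on linear extrapolation above 50% and on re-imaging depending only on 3-month LVEF.
3. Define the analysis set of each contrast by the two visits compared.

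The cost is SAP wording, one table shell and a more limited optional estimate. No new data are needed.

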7.9.6.4 Determination of Patients/Data for Analysis

At each visit, the subset of subjects part of the Enrolled Population with a LVEF measurement available at baseline and at the 3 months visit will be included in the analysis.

8. Safety Evaluation

Relatedness of adverse events using the CEC adjudication will be summarized using counts and percentages. Seriousness of adverse events using the Medtronic classification will be summarized using counts and percentages. Details of individual adverse events will be listed.

9. Changes to Planned Analysis

Any deviation from the analyses described in the statistical analysis plan and a justification for making the change, will be described in the clinical study report. Further, spurious data will be detected and fixed by data management, unused data will be reported in listings, missing data will be reported as count/percentage.

10. Validation Requirements

To ensure the quality of the statistical results and datasets created for the study, the following validation requirements will be implemented.

Programs that contribute directly or indirectly to results pertaining to the primary objective will be validated level I or level II by a statistician or a statistical programmer. Level II or Level III validation (self-validation) will be acceptable for programs, which do not pertain to the primary objective. The table below specifies the validation requirements for data extraction, mapped datasets, analysis datasets, TLGs (Tables, Listings, and Graphs) and study objectives. Mapped datasets are considered as datasets that map case report forms. Analysis datasets are considered to be datasets that contain derived variables relevant for the statistical analysis.

Table 11: Validation requirements

Program type	Level	Description
Extracts or creates datasets, e.g., mapped datasets	II	peer review
Generates analysis datasets	II	peer review
Generates Tables, Listings and/or Graphs (primary objective)	I or II	independent programming or peer review
Generates Tables, Listings and/or Graphs (non-primary objective)	II or III	peer review or self-validation
Implements statistical procedure	II or III	peer review or self-validation
Any other program	II or III	peer review or self-validation
Program previously validated with minor changes	III	self-validation

Summary of Changes

Version	Effective Date	Summary of Changes	Change Author
1.0	06-06-19	Initial Release
